**Figure 1: Study Schematic**

Visits 1 to 6

Visits 7 to Telephone 8

No dose reduction is permitted during the treatment periods.

Subjects unable to tolerate [REDACTED] TD-9855 will be discontinued from the study.

Assessments will be conducted as outlined in the Schedule of Study Procedures (Table 1). Refer to Appendix 6 and the Study Reference Manual for detailed instructions for conducting subject assessments in clinic and remotely. These instructions have been provided to ensure the method and conduct of each assessment is consistent across sites and subjects for both in clinic and remote visits.

At any time during the study, if a subject meets at least one of the following stopping rules, they must be discontinued and undergo an end of study visit:

- A determination from the PI (in discussion with the Sponsor’s medical monitor) that further administration of the investigational product may pose a safety concern to the subject.

- Sustained (at least 4 hours) SBP >180 mmHg or diastolic BP (DBP) >110 mmHg after 3 min of standing or after 5 mins in the sitting position, or a sustained (at least 4 hours) SBP >180 mmHg or DBP >110 mmHg measured in the supine state (head/torso elevated at approximately 30° from horizontal position).
- Intolerable AE, as determined by the PI.
- Subject becomes pregnant.

During the first 26 weeks, safety assessments will include a physical examination, neurological examination, vital signs (HR, BP, respiratory rate [RR] and body temperature), 12-lead electrocardiograms (ECGs), laboratory tests (hematology, chemistry, and urinalysis), Columbia Suicide Severity Rating Scale (C-SSRS), and monitoring of AEs. Safety assessments after Week 26 will include assessments of AEs and Concomitant Medications.

[REDACTED]

Subjects will be requested to refrain from making any significant dietary changes throughout the duration of the study. During their scheduled visits, subjects should be reminded to maintain an adequate fluid intake.

Subjects will complete the Early Termination Visit if they terminate from the study prior to Week 26. All subjects will complete the End of Treatment Visit (Visit 14) upon completion of the 182-week treatment period or if terminating early after Week 26. The Follow-up visit must be completed within 2 weeks (+/- 7 days) from the date of the last dose for all subjects who complete the 182-week treatment period or who terminate the study early at any point.

### 3.2. [REDACTED]

[REDACTED]

[REDACTED]

[REDACTED]

**3.3.** [REDACTED]

[REDACTED]

[REDACTED]

[REDACTED]

[REDACTED]

[REDACTED]

[REDACTED]

Based on the results of the human positron-emission tomography study in healthy volunteers,

[REDACTED]

### **3.4. Study Endpoints**

#### **Study Endpoints:**

Primary safety and tolerability endpoints include:

- Physical examination
- Neurological examination
- Vital signs
- Resting ECGs
- Clinical laboratory tests including biochemistry, hematology, and urinalysis.
- Concomitant medication
- AEs
- Subject compliance to study treatment
- Incidence of falls
- Columbia Suicide Severity Rating Scale (C-SSRS)

[REDACTED]

## **4. STUDY POPULATION**

This study will enroll adult subjects with confirmed symptomatic nOH due to MSA, PD, or PAF and who meet all of the applicable inclusion criteria and none of the applicable exclusion criteria defined below.

### **4.1. Inclusion Criteria**

Subjects who meet the following criteria will be eligible for study enrollment:

1. Completion of Study 0170 and, in the opinion of the Investigator, would benefit from long-term treatment with TD-9855.
2. The subject must be able to understand the nature of the study and must provide written informed consent prior to the conduct of any study procedures (including any changes occurring in the subject's current therapeutic regimen).
3. The subject must be willing to continue on treatment and must continue to meet all the inclusion criteria for the preceding study (Study 0170) except, a score of  $\geq 4$  in OHSA#1.

### **4.2. Exclusion Criteria**

Subjects who satisfy any of the following criteria are not eligible for study enrollment:

1. Subjects may not be enrolled in another clinical trial, with the exception of purely observational studies, which are allowed.
2. Psychiatric, neurological, or behavioral disorders that may interfere with the ability of subjects to give informed consent or interfere with the conduct of the study.
3. Medical, laboratory, or surgical issues deemed by the Investigator to be clinically significant.
4. Hypersensitivity to TD-9855 or the formulation excipients.

### **4.3. Pregnancy and Contraception**

#### **4.3.1. Females of Childbearing Potential**

Females of childbearing potential must have documentation of a negative pregnancy test prior to dosing.

Females are not considered to be of childbearing potential if they have had a total hysterectomy and/or bilateral tubal ligation or hysteroscopic sterilization (documentation for surgeries must be provided before enrollment) or are in a postmenopausal state (i.e., females who have had cessation of prior occurring menses for  $\geq 24$  months without alternative causes or females with premature ovarian failure).

#### 4.3.2. Contraception for Male and Female Subjects

All female subjects of childbearing potential and males who are able to father children must agree to abstain from sexual intercourse or to use a highly effective method of birth control during the study and for at least 30 days after the completion of study drug dosing (Section 6.9). A highly effective method of birth control is defined as one that results in a low failure rate (i.e., <1% per year) when used consistently and correctly. Such methods include:

- combined (estrogen and progestogen containing) hormonal contraception associated with inhibition of ovulation
  - oral
  - intravaginal
  - transdermal
- progestogen-only hormonal contraception associated with inhibition of ovulation
  - oral
  - injectable
  - implantable
- intrauterine device (IUD)
- intrauterine hormone-releasing system (IUS)
- bilateral tubal occlusion
- vasectomized partner provided that partner is the sole sexual partner of the female trial participant of childbearing potential and that the vasectomized partner has received medical assessment of the surgical success
- sexual abstinence is considered a highly effective method only if defined as refraining from heterosexual intercourse during the entire period of risk associated with the study treatments. The reliability of sexual abstinence needs to be evaluated in relation to the duration of the clinical trial and the preferred and usual lifestyle of the subject.

NOTE: Birth control methods which are not considered highly effective:

- progestogen-only oral hormonal contraception, where inhibition of ovulation is not the primary mode of action
- male or female condom with or without spermicide
- cap, diaphragm or sponge with spermicide

## 5. STUDY DRUG

All study drug supplied by the Sponsor must be stored in a secure location accessible only to designated study personnel.

### 5.1. [REDACTED]

#### 5.1.1. [REDACTED]

### 5.2. Dosage and Administration

All study drug will be administered orally without regard to food at approximately the same time each morning and taken with approximately 8 ounces of water.

### 5.3. Treatment Compliance

Subjects will be instructed to provide all used and unused study drug containers at each visit. Compliance with the dosing regimen will be assessed by reconciliation of used and unused study drug.

The subjects' dosing diary entries will also be reviewed at applicable study visits to assess compliance with study drug administration per documentation of the daily dosing times.

An example of the diary is provided in [Appendix 3](#).

Subjects with poor dosing compliance (i.e., < 80% or > 120%), as assessed by reconciliation of used and unused study drug and/or missing entries on the study drug administration diary, should receive counseling, assistance, and re-training as appropriate.

### 5.4. Drug Accountability and Reconciliation

The Investigator or designee is responsible for maintaining accountability records for all study drug(s) received from the Sponsor, in accordance with applicable government regulations and study procedures. The accountability record will include entries for receipt, distribution or dispensing, and destruction of the material(s). Unused and expired study drug will be disposed of in accordance with written instructions from the Sponsor.

## 6. STUDY PROCEDURES

### 6.1. Schedule of Study Procedures

The schedule of study procedures is summarized in [Table 1](#) and [Table 2](#). Assessments will be conducted as outlined in the Schedule of Study Procedures. Refer to [Appendix 6](#) and the Study Reference Manual for detailed instructions for conducting subject assessments in clinic and remotely. These instructions have been provided to ensure the method and conduct of each assessment is consistent across sites and subjects for both in clinic and remote visits.

### 6.2. Total Blood Volume

The total volume of blood to be drawn from each subject for safety laboratory tests is approximately [REDACTED]. Additional safety laboratory tests may be drawn as needed to manage any emergent health needs as directed by the Investigator.

### 6.3. Procedures by Visit

The Enrollment date for the Study is defined as Week 0/Visit 1.

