### SCHEDULE OF STUDY PROCEDURES

**Table 1: Schedule of Study Procedures (Visits 1 – 6)**

Each study visit for each subject may be conducted either in clinic or remotely									
Study Week (Visit/Telephone):	Week 0 Visit 1 (0170 Visit 9)	Week 2 Visit 2 +/- 3 days	Week 6 Visit 3 +/- 3 days	Week 10 Visit 4 +/- 7 days	Week 14 Telephone 1 +/- 3 days	Week 18 Visit 5 +/- 7 days	Week 22 Telephone 2 +/- 3 days	Week 26 Visit 6 +/- 7 days	Early Termination up to Week 26
Informed Consent	X								
Inclusion / exclusion criteria	X								
Medical history, including smoking history	X								
Concomitant Medications	X a	X	X	X	X	X	X	X	X
C-SSRS	X a	X	X	X		X		X	X
[REDACTED]	[REDACTED]	[REDACTED]	[REDACTED]	[REDACTED]		[REDACTED]		[REDACTED]	[REDACTED]
Vital signs (heart rate, blood pressure, respiratory rate and body temperature)	X a, b	X b	X b	X b		X b		X b	X b
Physical examination	X a			X				X	X
Neurological examination	X a			X				X	X
12-lead electrocardiogram e	X a			X				X	X
Pregnancy Test	X a, c			X c				X c	X c
Safety Labs (chemistry, hematology, urinalysis)	X a			X				X	X
Dosing, Incidence of Falls, and Midodrine Diaries	X a	X	X	X		X		X	X
Adverse Events	X a	X	X	X	X	X	X	X	X
Dispense Study Drug	X d	X d	X d	X d		X d		X d	
Study Drug Dosing	X d								
Collect Study Drug		X	X	X		X		X	X

a. Study 0170 procedures conducted at Visit 9 will serve as the baseline assessment for Visit 1 of Study 0171.  
 b. Vital signs will be assessed after the subject has been resting for at least 5 minutes in the seated or supine position.

- c. In women of childbearing potential only, urine beta human chorionic gonadotropin ( $\beta$ hCG) test will be performed and if positive, confirmation with serum  $\beta$ hCG test is required. The pregnancy test must be confirmed negative for a subject to be eligible for this study.
- d. Study drug will be ingested in the morning at approximately the same time of day with 8 ounces of water. The exact time and day of dosing will be recorded on the mornings of study visits. Subjects must be reminded to maintain an adequate fluid intake during their scheduled visits. Subjects will start taking study drug on the day after Visit 1.

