### **6.2. Baseline Definition**

In general, assessments obtained at Study 0170 Visit 9, which coincides with Study 0171 Visit 1, will serve as the baseline assessment for Study 0171. Subjects will start taking Study 0171 study drug on the day after Visit 1. If the start of Study 0171 dosing is delayed, however, the latest assessment obtained before the first Study 0171 dose will be used, even if obtained after Visit 1.

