### **6.3. Derived and Transformed Data**

#### **6.3.1. Study Day**

If the date of interest occurs on or after the date of first dose, Study Day will be calculated as (date of interest – date of first dose) + 1.

If the date of interest occurs before the date of first dose, Study Day will be calculated as (date of interest – date of first dose).

There is no Study Day 0. For analysis, Day 1 is defined as the day of the first study drug dose. The preceding day is Day -1.

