### **6.3.4. BMI (Body Mass Index)**

BMI is calculated as:

$$BMI (kg / m^2) = \frac{weight (kg)}{height (m)^2}.$$

BMI will be calculated using height as collected in Study 0169 or Study 0170 and weight as collected at Study 0170 Visit 9 (Day 154)/Study 0171 Visit 1 (Day -1).

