### **6.3.5. Visit Windows**

All assessments will be summarized using analysis windows. The term “out of window” will be applied to assessments that are outside the analysis windows, regardless of the visit label associated with the assessment in the EDC system.

The following visit windows will be used in the summarization of clinical data:

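### If the first dose is delayed, visits held early in the ±7-day allowance at Weeks 10, 18 and 26 fall outside the SAP windows and leave the by-visit safety summaries

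*Protocol*

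**What the plan says.** **Protocol.** Section 6.3 states: "The Enrollment date for the Study is defined as Week 0/Visit 1". Table 1 labels the same visit Week 0 and gives each later visit an allowance, for example "Week 10 Visit 4 +/- 7 days". Weeks 18 and 26 also have ±7 days; Weeks 2, 6, 14 and 22 have ±3. A footnote to the table adds: "Subjects will start taking study drug on the day after Visit 1". On treatment, laboratory tests and ECGs are scheduled only at Weeks 10 and 26. Vital signs are scheduled at Weeks 2, 6, 10, 18 and 26. Table 2 schedules none of these after Week 26.

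**SAP.** Section 6.3.1 uses a different origin: "For analysis, Day 1 is defined as the day of the first study drug dose". Table 4 gives Days 63–77, 119–133 and 175–189 for Weeks 10, 18 and 26. Section 6 limits summaries, unless noted otherwise, to data inside these windows. Section 6.3.5 applies the term out of window to "assessments that are outside the analysis windows, regardless of the visit label associated with the assessment in the EDC system". Section 6.2 anticipates a late start ("If the start of Study 0171 dosing is delayed") and then takes the latest pre-dose assessment as baseline. Neither 6.3.5 nor Table 4 makes a matching adjustment.

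**The concern.** The visit calendar seems to run from Visit 1 and the analysis calendar from first dose. They agree only when dosing starts exactly one day after Visit 1. The SAP recognises that this may fail and adjusts the baseline for it, but leaves the windows alone. Where allowance and window have the same width there is no slack, so any delay moves part of the permitted range out of the window.

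With only two scheduled on-treatment laboratory and ECG visits, losing one removes half of that subject's scheduled data from the change and shift tables (SAP 8.4) and the ECG summaries and threshold table (SAP 8.6), although the visit complied with the protocol. Laboratory tests, ECGs and vital signs are all listed as primary safety endpoints, in a study stopped early with 110 subjects enrolled.

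**Working it through.** **Inputs.** Visit 1 is date 0 (Protocol 6.3 and Table 1, with the anchor inferred from the Week 0 label). The first dose is at date 1 + d, where d is the delay beyond the planned day. A Week w visit falls at date 7w + j, with j from −7 to +7 at Weeks 10, 18 and 26 and from −3 to +3 at Weeks 2 and 6.

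**Formula.** By SAP 6.3.1, Study Day = (7w + j) − (1 + d) + 1 = 7w + j − d.

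**The plan's own figures.** Every Table 4 window is 7w ± 7. With d = 0, the permitted visits at Weeks 10, 18 and 26 span Days 63–77, 119–133 and 175–189, exactly the Table 4 windows. Slack is 0 days on both sides. At Weeks 2 and 6 the permitted visits span Days 11–17 and 39–45 inside windows 7–21 and 35–49, a slack of 4 days on each side.

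**With a delay.** Permitted visit days that fall outside their own window:

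| d | Week 10 study days | Weeks 10, 18, 26 | Weeks 2, 6 |
|---|---|---|---|
| 0 | 63–77 | 0/15 | 0/7 |
| 1 | 62–76 | 1/15 | 0/7 |
| 3 | 60–74 | 3/15 | 0/7 |
| 5 | 58–72 | 5/15 | 1/7 |
| 7 | 56–70 | 7/15 | 3/7 |
| 8 | 55–69 | 8/15 | 4/7 |
| 15 | 48–62 | 15/15 | 7/7 |

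The on-target visit (j = 0) has Study Day 7w − d, which falls below 7w − 7 only when d is 8 or more.

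**Dropped, not moved.** Days 50–62, 106–118 and 162–174 belong to no window. Each gap is 13 days long, so for d up to 13 a displaced Week 10, 18 or 26 visit lands in a gap and enters no by-visit summary.

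**Size, under stated assumptions.** The documents give no delay frequency. If visits are spread evenly and independently over the allowance, a delayed subject who attends both Weeks 10 and 26 loses at least one of them with probability 1 − (1 − d/15)²: 13%, 36% and 72% for d = 1, 3 and 7. If 5% to 20% of 110 subjects were delayed by 1 to 7 days, and all of them reached the visit, the expected loss per visit runs from 110 × 0.05 × 1/15 = 0.4 to 110 × 0.20 × 7/15 = 10.3 records.

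**Sensitivity to the anchor.**
- Visits timed from first dose with target Study Day 7w: a delay costs nothing.
- Visits timed as first dose plus 7w days: the latest permitted day (Day 78, 134 or 190) falls out even without delay.
- Visit 1 counted as Day 1, as Protocol 6.4.3.2 implies by putting the first dose on Day 2, with target Day 7w: the earliest permitted day (Day 62, 118 or 174) falls out even without delay.

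**The case against.** **The anchor is inferred.** The Protocol 6.3 sentence defines the enrolment date, not how visits are scheduled, and detailed visit instructions sit in manuals that are not public. This stands. The inference is still reasonable: Visit 1 is Week 0, and Table 4 matches Visit 1 plus 7w days exactly when there is no delay.

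**The trigger is off schedule and of unknown frequency.** The protocol dispenses drug at Visit 1 and starts dosing the next day; SAP 6.2 is a contingency, not evidence that delays occurred. This stands and limits the severity.

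**The loss is partial.** A reader might infer that a one-day delay removes the Week 10 or Week 26 data of every late starter. It does not: it removes only a visit held exactly 7 days early, and visits held late in the allowance are protected.

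**A selective loss might be inferred for remote subjects supplied by courier.** Protocol Appendix 6 says a courier ships drug, but nothing says it arrives after Visit 1 or that these subjects start late. The documents do not support that link.

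**Safety signals are not hidden.** All data stay in listings, with abnormal laboratory values and extreme vital signs flagged. The separate QTcF listing covers postbaseline values and is not tied to a visit. Adverse events, exposure and falls do not use the Table 4 visit windows. This stands; the effect is on by-visit descriptive tables.

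**Text is redacted directly after the window rule in SAP 6.** It may hold a relevant exception, so the absence of one can be asserted only for the visible text.

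**Conclusion.** The point holds as a minor one. Given a Visit 1 anchor, the date arithmetic leaves no doubt: a first dose d days late puts the earliest d of 15 permitted days at Weeks 10, 18 and 26 out of window, for d up to 15. Compliant laboratory and ECG records (Weeks 10 and 26) and vital-sign records (Weeks 10, 18 and 26) then leave the by-visit summaries but remain in the listings. Weeks 2 and 6 are affected only from d = 5.

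Two things are not established: that sites scheduled from Visit 1, and how many subjects started late. The 13% to 72% range applies to a single delayed subject under an even-spread assumption. The range of 0.4 to 10 records per visit rests on an assumed share of delayed subjects and, because the study was terminated early, probably overstates how many reached each visit. Neither is an estimate of what happened. A stronger conclusion, that the overall safety evaluation is compromised, does not follow.

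**What to change.** **Change, in SAP 6.3.5 before database lock.** State the anchor from which visits were scheduled, and add a rule: a scheduled visit held within its protocol allowance counted from Visit 1 is assigned to its nominal week even if its study day lies outside Table 4, provided the record was obtained after the first Study 0171 dose and is not used as baseline. Footnote the number of subjects whose first dose came later than one day after Visit 1.

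The proviso is needed. At d = 11 the first dose is at date 12, so a permitted Week 2 visit at date 11 precedes it and could serve as baseline under SAP 6.2.

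**Alternative.** Make the windows contiguous for each assessment. For example, with laboratory and ECG windows of Days 2–126 for Week 10 and Day 127 onward for Week 26, no permitted visit leaves its window for delays up to 61 and 48 days. With vital-sign windows of Days 2–28, 29–56, 57–98, 99–154 and 155 onward, Week 10 is the tightest and is safe up to 6 days. Wider windows would also admit more unscheduled and early-termination records.

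**Cost.** One or two sentences, one derived field from dates already collected, and one footnote. For late starters the nominal week overstates time on drug by d days, which the footnote makes visible. The first option also moves the SAP closer to Protocol 8.5, which calls for summaries by nominal visit. Because the study has been terminated, there is no practical value in amending the protocol's visit schedule.

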#### 6.3.1. Screening

All subjects enrolled into Study 0171 will roll over from Study 0170, therefore there is no screening visit. Study 0170 procedures conducted at Visit 9 will serve as the baseline assessments for Visit 1 of Study 0171.

#### 6.3.2. Visit 1 – Week 0

Study 0170 procedures conducted at Visit 9 will serve as the baseline assessments for Visit 1 of Study 0171.

Beginning on the day after Visit 1, subjects will receive a single dose of [REDACTED] TD-9855 [REDACTED] and continue thereafter for the 182-week duration of the treatment period.

The following procedures must be completed first, and in the order below at the Week 0 Visit:

1. Written informed consent (signed and dated) after the nature of the study has been explained and before any study procedure is performed
2. Review of protocol inclusion and exclusion criteria prior to beginning subject evaluations
3. Medical history, including smoking history
4. Review concomitant medications

The following procedures are listed in the recommended order, however flexibility for scheduling is permitted:

5. C-SSRS
6. [REDACTED]
7. Vital signs
  - a. HR, systolic BP (SBP), and diastolic BP (DBP)
  - b. Respiratory rate (RR) and body temperature

8. Physical examination
9. Neurological examination
10. 12-lead ECG (in triplicate separated by at least 1 minute for each replicate, after the subject has been resting for at least 5 minutes)
11. Pregnancy test (in women of childbearing potential only)
12. Blood collection:
  - a. Hematology
  - b. Chemistry
13. Urine collection: Urinalysis
14. Dosing Diary dispensation
15. Incidence of Falls Diary, dispensation and review of diary completion instructions
16. Midodrine Diary dispensation
17. AE assessment (AEs, SAEs, adverse event of special interest [AESIs])
18. Dispense study drug

**6.3.3. Visit 2 – Week 2**

The following procedures will be performed at the Week 2 visit:

1. Review concomitant medications
2. C-SSRS
3. [REDACTED]
4. Vital signs
  - a. HR, SBP, and DBP
  - b. RR and body temperature
5. Dosing Diary collection and review
6. Incidence of Falls Diary collection and review
7. Midodrine Diary collection and review
8. AE assessment (AEs, SAEs, AESIs)
9. Collect, review, and dispense study drug

